6.1 Analysis Plan

Aim 1A:

We will assess whether primary and secondary outcomes are significantly different in the experimental and usual care groups using the generalized estimating equations (GEE) approach with an unstructured working correlation matrix to adjust for clustering. We will perform multivariate analyses using GEE adjusting for covariates such as baseline compliance with HH and frequency of Contact Precautions. Analyses will be conducted at the level of the participating unit and will follow the intention to treat approach.

Aim 1B:

The primary analysis will be an intention-to-treat analysis where the gloved hands of HCWs sampled in the usual care group will be compared to those in the Intervention group regardless of HH activity. A secondary, as-treated analysis will be performed where HCWs who were observed to perform HH and then don gloves will be compared to those in which gloves were directly applied without performing HH. The primary, intention-to-treat analysis will provide great insight into the effectiveness of this intervention while the secondary, as-treated analysis will validate efficacy.

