The primary outcome, total bacterial colony forming units (CFUs) > 30 of gloved hands, will be compared between the two groups using a comparison of proportions. In this case a one-sided $p < 0.025$ will be statistically significant for noninferiority. We will also compute a two-sided 95% confidence interval for the relative risk of CFUs > 30 comparing direct gloving to HH + gloving, where the upper bound of the confidence interval < delta will be considered statistically significant. In this analysis, we define the non-inferiority margin, or delta, equal to 1.15. We feel (in consultation with microbiologists and HH experts) that if glove reuse (intervention) were found non-inferior to usual care by a 1.15 margin (i.e. a difference of 15%) that this would be enough to lead to change in practice. Robust empirical standard errors will be calculated using generalized estimating equations with an independence working correlation matrix to account for within-site clustering for sample proportions. A secondary analysis will compare groups using CFUs as a count outcome. We will compute a two-sided 95% confidence interval for the relative mean of CFUs on gloved hands comparing the intervention to the usual care group. The upper bound of the confidence interval < delta will be considered statistically significant, where delta is 1.15. The secondary outcomes, presence of pathogenic bacteria and total number of pathogenic and non-pathogenic bacteria present, will be analyzed like the primary outcome.

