6.2 Sample Size Estimates

Aim 1A:

How many participants (or specimens, or charts) will be used in this study?

UMMC: 6 units Worldwide: 14 units

14 units will be randomized to intervention or usual care. Over the 12-month study period we expect a minimum of 7000 total observations (14 units across the systems x 500 observations). Each system will have a research coordinator perform observations 3 hours per day four days per week. We estimate an average of 5 observations per hour¹⁹ (15 per day and 60 per week) and thus over 2500 observations per year per research coordinator are feasible (we expect to require fewer to achieve desired power). Average HH compliance is consistently at 40-50% and are often lower when glove use is indicated^{1,15}, we believe the compliance with infection prevention practices (i.e. primary outcome, composite compliance with HH AND glove use) in the usual care group will be ~40%. Recent studies have shown compliance with gloves when indicated to be approximately 70-80%¹⁵. Thus for the primary outcome, we expect a difference in compliance with infection prevention practice to be ~ 30%. If we assume 500 observations per area, an alpha level of 0.05, an interclass coefficient of 0.001²² we will require inclusion of 4 patient care areas (2 experimental and

2 usual care) to achieve a power greater than 90% power to detect an effect size of 30% (i.e. the primary outcome). If we vary the interclass coefficient to 0.01, we still have greater than 90% power under the same conditions. Relative to the secondary outcome, in which we will compare compliance with gloving only in both the direct gloving (i.e. experimental group) and the usual care group, we believe it is reasonable to expect that removing the cumbersome and time-consuming requirement of HH prior to glove use may increase compliance with glove use when indicated by approximately 10%. Using the same assumptions as the primary aim with an interclass coefficient of 0.001, we need to recruit and randomize 4 participating units to achieve > 90% power to detect this effect size of 10%. If we use the higher interclass coefficient of 0.01, we need 8 participating units to achieve > 85% power. So in short, we have ample power to see an effect in both primary and secondary outcomes including the sub-populations of adult ICU, dialysis and emergency department.

Aim 1B:

How many participants (or specimens, or charts) will be used in this study?

Local: 866 Worldwide: 2600

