Based on pilot data, we anticipate 5% of HCWs in the usual care group (hand-hygiene plus gloves) and 3.5% in the experimental group (direct gloving) to have > 30 CFUs. We define non-inferiority as a relative risk < 1.15 of having > 30 CFUs, comparing the experimental group to the usual care group. That is, delta equal to 1.15. Under these assumptions, 1280 samples (per group) are sufficient for a one-sided test with alpha=0.025 to have 80% power to detect noninferiority.²³ 1280 samples in both groups will result in a total of 2560 samples for the 12-month study period. Spread across the 14 proposed participating units at the 3 healthcare systems (UMMC and STC will share a Research Associate), this is approximately 850 samples per site and 180 samples per participating unit over the 12-month study period. Thus, each site will need to recruit just over 70 HCWs each month to meet the goal sample size. In the pilot study 230 HCWs were recruited and agreed to participate in a single month.

7 Data Collection, Handling and Storage

All data collected will be stored in a relational database in order to digitize the data for analysis. No PHI will be collected. The database will be stored on a shared drive. Data from University of Iowa and Johns Hopkins Hospital will be sent electronically the investigators at the University of Maryland – data from Aim 1A is aggregate unit level data and not-human subjects data; and data from Aim 1B is completely de-identified.

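### The 80% power stated for Aim 1B assumes that every sampled usual-care worker did hand hygiene, but the primary analysis compares arms whatever hand hygiene was done; across plausible adherence the power is below 80%

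*Combined protocol and SAP*

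**What the plan says.** Section 6.1, Aim 1B, makes the intention-to-treat (ITT) comparison primary: "HCWs sampled in the usual care group will be compared to those in the Intervention group regardless of HH activity". An as-treated comparison of HH-then-glove with direct gloving is secondary, and the two are given different roles: the ITT result speaks to effectiveness, while "the secondary, as-treated analysis will validate efficacy".

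The same section describes the deciding interval as one for the "relative risk of CFUs > 30 comparing direct gloving to HH + gloving". Its margin sentence, however, speaks of the intervention as if it "were found non-inferior to usual care by a 1.15 margin".

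Section 6.2, Aim 1B, gives the power inputs: "we anticipate 5% of HCWs in the usual care group (hand-hygiene plus gloves) and 3.5% in the experimental group (direct gloving"). The margin is a relative risk (RR) of 1.15, "comparing the experimental group to the usual care group", and 1,280 samples per group are called "sufficient for a one-sided test with alpha=0.025 to have 80% power to detect noninferiority". Section 6.2 attributes the two rates to pilot data. Section 1.2 describes the pilot's groups by whether HH was or was not performed before gloving.

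For Aim 1A, section 6.2 expects "composite compliance with HH AND glove use) in the usual care group will be ~40" per cent, a difference of about 30 points in the composite outcome, and a gain of about 10 points in glove use. It also cites glove compliance of 70–80% from earlier studies.

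**The concern.** The power calculation uses rates defined by what was done to the hands, whereas the primary test compares arms. The two agree only if nearly all sampled usual-care workers do HH before gloving. The trial's premise is that many do not, and the Aim 1A figures build that in. Section 6.2 states no adherence assumption for Aim 1B.

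Two things are at stake. First, the plan expects direct gloving to have the lower contamination rate. Usual-care workers who skip HH then pull the usual-care rate down towards the intervention rate, and non-inferiority becomes harder to show than the stated 80% suggests. Second, the wording used for the primary interval invites a reader to take an ITT result as the answer to whether skipping HH is non-inferior to doing it, which is a different question from whether the unit-level policy is non-inferior.

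**Working it through.** **Inputs.** From section 6.2, Aim 1B: rates of 5% and 3.5%, margin RR 1.15, one-sided 0.025, n = 1,280 per group. From section 6.2, Aim 1A: about 40% HH and gloves in usual care, a 30-point composite difference, a 10-point glove gain. From section 4.2: only workers who have donned gloves are sampled. Clustering is ignored throughout.

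**1. The plan's own figure.**

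- Difference scale: the margin is 0.15 × 5% = 0.75 points and the expected difference is −1.5 points, so the distance to the margin is 0.0225. Required n = (1.960 + 0.842)² × (0.05 × 0.95 + 0.035 × 0.965) / 0.0225² = 7.849 × 0.081275 / 0.00050625 = about 1,260. At 1,280 the standard error is √(0.081275/1,280) = 0.00797, and power is Φ(0.0225/0.00797 − 1.960) = Φ(0.864) = 80.6%. This reproduces the plan.
- Log-RR scale, matching the rule that the upper limit of the RR interval must be below 1.15: ln(1.15 × 0.05/0.035) = 0.4964. The standard error is √[(0.95/0.05 + 0.965/0.035)/1,280] = 0.1907. Power is Φ(2.603 − 1.960) = 74.0%.

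Both give the entire usual-care arm the 5% rate.

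**2. Share of gloved usual-care hands without HH.** The composite in the intervention arm is glove use alone, so gloving there is 40 + 30 = 70%. Gloving in usual care is then 70 − 10 = 60%. Among gloved usual-care workers, 40/60 = 67% did HH and s = 33% did not. Applying the cited 70–80% glove use directly to usual care would give s = 1 − 40/70 = 43% to 1 − 40/80 = 50%, but that does not fit the 30-point and 10-point figures together.

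**3. Power at s = one third.** Assume that workers who skip HH carry the 3.5% rate and that no intervention worker does HH. The usual-care rate is 2/3 × 5% + 1/3 × 3.5% = 4.5%, and the arm-level RR is 3.5/4.5 = 0.778.

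- Difference scale: the margin is 0.15 × 4.5% = 0.675 points and the distance is 0.00675 + 0.010 = 0.01675. The standard error is 0.00774. Power is Φ(2.163 − 1.960) = 58.0%.
- Log-RR scale: ln(1.15 × 0.045/0.035) = 0.3911, with standard error 0.1952. Power is Φ(2.003 − 1.960) = 51.7%.

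**4. Range.** The same formulas with usual-care rate 0.05(1 − s) + 0.035s:

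| No-HH share s | Usual-care rate | Arm-level RR | Power, difference | Power, log-RR |
|---|---|---|---|---|
| 0 (as planned) | 5.00% | 0.700 | 80.6% | 74.0% |
| 10% (assumed) | 4.85% | 0.722 | 74.8% | 68.0% |
| 20% (assumed) | 4.70% | 0.745 | 68.1% | 61.3% |
| 33% (40/60) | 4.50% | 0.778 | 58.0% | 51.7% |
| 43% (40/70) | 4.36% | 0.803 | 50.3% | 44.6% |
| 50% (40/80) | 4.25% | 0.824 | 44.4% | 39.3% |

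If the margin is held at 0.75 points instead of scaling with the usual-care rate, s = 33% gives 61.8%. If 10% of sampled intervention staff still did HH (an assumption), their arm's rate is 0.9 × 3.5% + 0.1 × 5% = 3.65%, and s = 33% gives 50% or 44%.

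**5. What the margin means for the HH contrast.** If direct gloving versus HH + gloving has relative risk R, the arm-level RR is R/[(1 − s) + sR]. Setting this to 1.15 at s = 1/3 gives R = 1.15 × 0.667/(1 − 1.15 × 0.333) = 0.767/0.617 = 1.24. This bears on interpretation only.

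**The case against.** Several points on the other side stand.

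- **The plan does assign roles.** Section 6.1 gives the ITT analysis to effectiveness and the as-treated analysis to efficacy. A reader might infer that the plan leaves open which analysis supports which conclusion; it does not. The split could only be tied more explicitly to the 1.15 margin.
- **The interval label may be shorthand.** Section 6.2 uses HH plus gloves and direct gloving in parentheses as names for the arms, and the margin sentences refer to the arms. The label is ambiguous rather than proof that another analysis was meant. The power input does not depend on how the label is read.
- **The error rate is not inflated.** A reader might infer that the 2.5% level is lost, because a direct-gloving versus HH + gloving RR of exactly 1.15 would pass more often than that. But at s = 1/3 this corresponds to an arm-level RR of 1.15/(2/3 + 1.15/3) = 1.15/1.05 = 1.095, which lies inside the arm-level margin. The ITT test targets the arm-level null, and dilution does not disturb its level there.
- **One third is inferred.** It chains three approximate Aim 1A figures for all Contact Precaution room entries. Section 3 has usual-care staff taught to do HH before gloving. Section 5.1 has investigators introduce themselves as staff approach the room (section 3 has the approach come after gloving). Either could raise HH among those sampled, so one third is a point in a range.
- **The loss depends on direct gloving being better.** If the true RR were 1, dilution would change nothing: with 5% in both arms, power is about 14% (difference) or 13% (log-RR) at any share. But 3.5% versus 5% is the plan's own assumption, and its 80% rests on it.

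It is also tempting to set 52% against 80%. That mixes scales: 74% is the log-RR figure before any dilution.

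**Conclusion.** The point holds. The stated 80% is correct arithmetic for full HH in the usual-care arm and none in the intervention arm, but the primary ITT comparison does not require either, and the plan's own figures point to incomplete usual-care adherence. On like-for-like scales, a one-third no-HH share takes power from 80.6% to 58% or from 74% to 52%, about 22 points either way. At an assumed 10–20% share, power is 75–68% or 68–61%, still below 80%.

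This rests on four assumptions: usual-care workers who skip HH have the 3.5% rate, intervention workers do no HH, clustering is ignored, and the 5% is a rate for hands that had HH, as section 6.2's parenthesis and the pilot's description in section 1.2 suggest. The exact share is uncertain. The direction is not, so long as direct gloving is the better arm as the plan anticipates.

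ITT remains a sound primary analysis for the unit-level policy. Nothing here shows that it should be replaced or that its type I error is wrong.

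**What to change.** 1. In section 6.2, Aim 1B, restate power over a stated range of usual-care HH adherence, for example 50% to 90% of sampled staff, and name the scale used. On the assumptions above, 50% to 90% adherence gives 44–75% (difference) or 39–68% (log-RR).
2. In section 6.1, label the primary interval as *comparing the intervention group with the usual care group*.
3. Add to section 6.1: *An ITT upper bound below 1.15 supports non-inferiority of the unit-level direct-gloving policy. Statements about direct gloving versus HH + gloving rest on the as-treated relative risk, described as non-randomised.* Covariate adjustment of the as-treated analysis can be left optional.
4. Report the proportion of sampled workers who did HH, by arm. Section 3 already records this for each sample.

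The cost is wording and one table, with no new data and no added samples. The downside is a less favourable stated power, a narrower ITT conclusion, and an HH contrast that rests on a non-randomised estimate. That estimate is also short of 80%: at a one-third share, 1,280 × 2/3 = 853 hands with HH face 427 + 1,280 = 1,707 without. On the log-RR scale the standard error is √[0.95/(853 × 0.05) + 0.965/(1,707 × 0.035)] = 0.196, and power is Φ(0.4964/0.196 − 1.960) = about 72% before any confounding. For information only, 80% ITT power at a one-third share would need about 2,148 (difference) or 2,505 (log-RR) per group.

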We will perform a nested, multicenter validation study in which we will randomly sample the gloved hands of HCWs entering Contact Precaution-patient rooms in both the intervention and usual care units. Sampling will occur at random and HCWs will not be told in advance that sampling will be performed. A research team member will approach potential participants immediately after gloves are donned and just prior to entering a Contact Precaution-patient room. HCWs will be asked if they have participated in this study previously and those that answer yes will be excluded from participation. Gloved hands of willing HCWs will be sampled via direct imprint of the non-dominant gloved hand onto an agar plate. In addition to sampling of gloved hand, additional data will be collected regarding the date, time and location of the observation, whether the unit was allocated to intervention or usual care, whether the HCW performed HH prior to donning non-sterile gloves, the HCW role (e.g. RN, MD, etc...), when the HCW had started their shift and the time since last performing HH. Each sample will be given a unique number, however, there will be no link to HCW participants and no identifying information will be collected. After sampling, agar plates will be assessed for microbial content including total colony counts and identification of specific pathogenic bacteria including *Staphylococcus aureus*, *Enterococcus*, *Enterobacteriaceae*, *Pseudomonas aeruginosa* and *Acinetobacter baumannii*.

4 Selection and Withdrawal of Participants

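### The secondary Aim 1B as-treated comparison is non-randomised and no adjustment is specified for it, although location, role and shift start are recorded; strong confounding could shift its relative risk by about the 1.15 margin

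*Combined protocol and SAP*

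**What the plan says.** Section 6.1, Aim 1B, makes the intention-to-treat comparison of allocated groups primary. It then adds a secondary comparison in which "HCWs who were observed to perform HH and then don gloves will be compared to those in which gloves were directly applied" without HH, and states that "the secondary, as-treated analysis will validate efficacy".

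The method appears in the next paragraph of Section 6.1. The proportion with more than 30 CFUs "will be compared between the two groups using a comparison of proportions", with robust errors from "generalized estimating equations with an independence working correlation matrix to account for within-site clustering for sample proportions". Non-inferiority is judged against a relative risk (RR) margin of 1.15 at one-sided 0.025.

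Covariate adjustment is described in Section 6.1 for Aim 1A only: "We will perform multivariate analyses using GEE adjusting for covariates such as baseline compliance with HH and frequency of Contact Precautions". Aim 1B has no counterpart.

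Section 3, Aim 1B, shows what is recorded with each glove sample: "additional data will be collected regarding the date, time and location of the observation", the unit's allocation, whether HH was performed, and "the HCW role (e.g. RN, MD, etc...), when the HCW had started their shift and the time since last performing HH". Allocation and HH status define the two comparisons. The other items are given no use in the Aim 1B analysis.

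**The concern.** Randomisation protects the allocated groups. It does not protect groups defined by what workers did at the door. The direct-gloving group pools intervention workers following their instruction with usual-care workers who omitted a step they were taught. Omission may depend on unit type, role and hours into the shift, and so may glove contamination. Robust errors with an independence working matrix change the standard error; they leave the confounded estimate where it is.

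This matters because the analysis is asked to validate efficacy and is the plan's only comparison of the two practices as performed. If direct gloving did raise contamination, the intention-to-treat contrast would be diluted, since many usual-care workers would also glove directly. Readers will look to the as-treated result as the check on that. Confounding could make it pass or fail the margin for reasons unrelated to HH.

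**Working it through.** **The plan's own figure.** No figure is stated for the as-treated groups. The stated 1,280 per group belongs to the intention-to-treat contrast. On the difference scale, (1.960 + 0.842)² × (0.05×0.95 + 0.035×0.965) / (1.15×0.05 − 0.035)² ≈ 1,260, which is 1.6% below 1,280, so it reproduces. It is used below as the number sampled per arm.

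**Step 1: who is in the direct-gloving group.** Section 6.2 expects about 40% composite compliance and 70-80% glove use. Among gloved usual-care workers, HH is then 40/70 = 57% (40/80 = 50% at the other end). HH before gloving in intervention units is not given; assume 10-25%. The share of the direct-gloving group that comes from usual care is (1 − HH in usual care) / [(1 − HH in usual care) + (1 − HH in intervention)]:

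- 57% and 10%: 0.429/(0.429 + 0.90) = 32%
- 57% and 25%: 0.429/(0.429 + 0.75) = 36%
- 50% instead of 57%: 36-40%

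**Step 2: confounding by unit type, true RR of 1.** The 14 units split 4, 3, 4, 3 by type (Section 3). Everything else here is assumed:

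- usual-care HH of 35, 50, 65 and 75% in the four types (mean 55%);
- contamination of 3, 4, 6 and 8%, in the same or the reverse order;
- equal sampling per unit and the same type mix in both arms.

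The assignment of values to types is arbitrary.

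Worked case, intervention HH flat at 10%, in units of one unit's samples per arm:

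- HH group: 4×0.45, 3×0.60, 4×0.75, 3×0.85 = 1.80, 1.80, 3.00, 2.55 (total 9.15)
- Direct group: 4×1.55, 3×1.40, 4×1.25, 3×1.15 = 6.20, 4.20, 5.00, 3.45 (total 18.85)
- Dirtier types do more HH: risks 51.0/9.15 = 5.57% (HH) and 93.0/18.85 = 4.93% (direct), RR 0.89
- Dirtier types do less HH: 44.85/9.15 = 4.90% and 105.15/18.85 = 5.58%, RR 1.14

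Unadjusted RR when the true RR is 1, for intervention HH averaging 10-25% (the ranges also cover contamination of 3, 4, 5, 8%):

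| Assumption | Dirtier types do less HH | Dirtier types do more HH |
|---|---|---|
| Intervention HH flat across types | 1.12-1.14 | 0.89-0.90 |
| Intervention HH varies in step with usual care | 1.17-1.19 | 0.85-0.87 |
| Mild spreads (contamination 4-6%, HH 50-65%) | up to 1.03 | down to 0.97 |

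Perfect ordering is the extreme. Over all 24 pairings of the 3, 4, 6, 8% pattern with the four HH levels, the median RR is 0.99. In a simulation of 14 units with contamination and HH varying independently, a between-unit log-risk SD of 0.4 gives a 5th-95th percentile range of 0.85-1.18, and an SD of 0.2 gives 0.92-1.09.

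**Step 3: false non-inferiority.** Set the true RR to 1.15, with dirtier types doing more HH. The probability of declaring non-inferiority is Φ[(ln 1.15 − ln RR)/SE − 1.96], where RR is the confounded value and SE² = (1−pH)/(nH·pH) + (1−pD)/(nD·pD), with H the HH group and D the direct group. It is about 10% with flat intervention HH and 12-16% when it varies in step, against a nominal 2.5%. This SE ignores clustering.

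**Step 4: confounding by role.** Assume a role with double the risk makes up 20% of the HH group and 40% of the direct group. Then RR = (0.6 + 0.4×2)/(0.8 + 0.2×2) = 1.4/1.2 = 1.17. Weaker cases give less: a risk ratio of 1.5 at 30% versus 50% gives 1.25/1.15 = 1.09, and 1.25 at 30% versus 40% gives 1.10/1.075 = 1.02.

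**The case against.** **Silence is not exclusion.** Section 6.1 defines the as-treated groups but writes out no model for them, and nothing says the recorded covariates will go unused. This stands. A reader might infer that the plan commits to a crude comparison, and the documents do not go that far. What they support is that no adjustment is specified. That still leaves the model open to choice after the data are seen.

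**The design limits the bias.** Randomisation is stratified by unit type, units within a type are chosen for similar baseline compliance, and most of the direct-gloving group comes from randomised intervention units. This stands in part. Those features balance the allocated arms and narrow differences within a type. They do not balance unit type or role between workers who did and did not perform HH.

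**The size is assumed.** This stands. The larger shifts need strong, well-ordered confounding, and mild spreads shift the RR by 3% or less.

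**The analysis is secondary.** This also stands. The primary analysis is intention-to-treat, and the sample size is not stated for the as-treated groups.

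**Adjustment has limits.** At 5% there are about 128 events in 2,560 samples; at the planned 5% and 3.5%, about 64 + 45 = 109. Section 6.1 clusters by site, and Section 6.2 counts samples per site over three health systems. Robust errors on so few clusters cannot support a model that also has hospital as a covariate. The fix must therefore keep the model small and name the cluster.

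**Conclusion.** The point holds as a cheap improvement to a secondary analysis. The as-treated contrast is non-randomised, about a third of its direct-gloving group would be self-selected usual-care workers, and no adjustment is specified although the main covariates are collected. Under strong confounding the bias can approach or reach the 1.15 margin in either direction (about 1.12-1.19 or 0.85-0.90 by unit type, 1.17 by role); under mild confounding it is negligible. All of these rest on assumed contamination and HH levels by unit type or role, and on assumed HH of 10-25% in intervention units.

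Two stronger readings are not supported. A reader might infer that the as-treated RR will be off by 15%; the documents give no unit-type or role data from which to say so. A reader might also infer that the primary Aim 1B conclusion is confounded in the same way; it compares allocated groups and is not affected by this point.

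**What to change.** In Section 6.1, Aim 1B:

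- Specify the as-treated RR from a log-link (modified Poisson) GEE adjusted for unit type, HCW role and hours since shift start, adding hospital only if the number of events allows.
- Cluster by the 14 units, with a small-sample correction to the robust errors.
- Do not adjust for time since last HH: performing HH before gloving resets it, so it is part of the exposure.
- Report a within-unit (unit-stratified) estimate as a sensitivity analysis.
- Replace the claim that the analysis validates efficacy with a description of it as supportive, non-randomised evidence.

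The cost is a few sentences and one model. No new data are needed, since every covariate is already recorded. The interval will be somewhat wider, and residual confounding by unrecorded factors remains, which is why the wording should change as well as the model.

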Hypothesis 1: When compared to the standard practice of performing HH and then donning gloves, directly gloving when non-sterile gloves are indicated will increase compliance with HH and glove use and will have no effect on bacterial contamination of gloves (i.e. total bacterial colony counts).

Aim 1a: Perform a multicenter, cluster-randomized trial to evaluate the efficacy of a direct gloving strategy to improve compliance with infection prevention practices (i.e. HH and glove use).

Aim 1b: Perform a nested multicenter validation study, where gloved hands of healthcare providers will be randomly sampled to determine bacterial contamination of non-sterile gloves after donning.

1 Background Information and Rationale

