1.5 Risk Benefit Ratio

The potential benefits of this study outweigh the minimal risks to participants.

2 Study Objectives, Aims and Hypothesis

Aim 1A: Perform a multicenter, cluster randomized trial to evaluate the efficacy of a direct gloving strategy to improve compliance with infection prevention practices (i.e. HH and glove use).

Hypothesis: When compared to the standard practice of performing HH and then donning gloves, directly gloving when gloves are indicated will increase compliance with HH and glove use.

Aim 1B: Perform a nested multicenter validation study, where gloved hands of HCWs will be randomly sampled to determine bacterial contamination of non-sterile gloves after donning.

Hypothesis: When compared to the standard practice directly gloving when gloves are indicated will have no effect on bacterial contamination of gloves.

3 Study Design and Procedure

Aim 1A:

Study Design: We will perform a cluster-randomized trial to include 14 patient care areas (i.e. units) at the University of Maryland Medical Center (UMMC), the R Adams Cowley Shock Trauma Center (STC), University of Iowa Hospitals (UIH), and Johns Hopkins Hospital (JHH). Each unit will be randomly assigned to the intervention or usual care group. Randomization will be stratified by unit type: adult intensive care, general pediatric wards, emergency departments and inpatient hemodialysis units. One unit from each of the four types at UMMC, UIH, and JHH will be selected for study participation and will be randomized; and two units (one Adult ICU and the Trauma Resuscitation Unit (comparable to the Adult ED)) will be selected and randomized from Shock Trauma. We have specifically chosen these diverse areas to avoid any potential crossover of effect from one study unit to another as units have very different personnel with very little crossover of care.

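### The 80% power for Aim 1B assumes direct gloving cuts the CFU > 30 rate by 30%; under the hypothesised absence of effect, the stated relative-risk rule has about 12.5% power

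*Combined protocol and SAP*

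**What the plan says.** Hypothesis 1 in the Summary states that direct gloving "will have no effect on bacterial contamination of gloves (i.e. total bacterial colony counts"). Section 2 repeats it for Aim 1B: "directly gloving when gloves are indicated will have no effect on bacterial contamination of gloves".

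The Aim 1B endpoint in section 6.1 is a dichotomy of that count, "The primary outcome, total bacterial colony forming units (CFUs) > 30 of gloved hands". The decision uses a two-sided 95% interval for the relative risk, "where the upper bound of the confidence interval < delta will be considered statistically significant", with delta 1.15. Section 6.2 gives the same margin: "We define non-inferiority as a relative risk < 1.15 of having > 30 CFUs". The count itself comes second: "A secondary analysis will compare groups using CFUs as a count outcome", also with delta 1.15.

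For the sample size, section 6.2 says that, on pilot data, "we anticipate 5% of HCWs in the usual care group (hand-hygiene plus gloves) and 3.5% in the experimental group (direct gloving") will exceed 30 CFU, and that 1,280 samples per group are "sufficient for a one-sided test with alpha=0.025 to have 80% power to detect noninferiority". It gives no power for equal rates. Section 6.1 provides robust standard errors for within-site clustering, but section 6.2 includes no allowance for clustering in Aim 1B.

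**The concern.** A non-inferiority trial is usually planned at the effect it expects to find. Aim 1B expects none, yet its sample size is planned at a 30% reduction in risk. The event is expected in only 3.5% to 5% of samples and the margin is tight in relative terms, so power depends heavily on that assumed benefit. The 80% therefore does not describe the trial's chance of success under its own hypothesis.

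The plan relies on Aim 1B to replicate the pilot's safety finding and to support a change in guidelines. If direct gloving makes no difference, the most likely primary result is a failure to show non-inferiority. The plan does not say how such a result is to be read.

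**Working it through.** **Inputs.** From sections 6.1 and 6.2: 1,280 per group; rates of 5% (usual care) and 3.5% (direct gloving); margin RR 1.15; one-sided alpha 0.025; 14 units. From the Summary and section 2: no effect, so RR = 1. Constants: ln 1.15 = 0.1398; ln 0.70 = -0.3567; z = 1.96 and 0.8416.

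**1. The plan's own figure.** Read 15% of 5% as a risk-difference margin of 0.0075. The distance from the assumed difference to the margin is 0.015 + 0.0075 = 0.0225. In the Farrington-Manning score test, the rates constrained to the margin are 3.97% and 4.72%, giving a null variance of 0.08305. The alternative variance is 0.05 × 0.95 + 0.035 × 0.965 = 0.08128.

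n = (1.96 × √0.08305 + 0.8416 × √0.08128)² / 0.0225² = 1,279.4, so 1,280 per group. The stated figure is reproduced, but on the risk-difference scale.

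**2. The stated rule at the assumed rates.** On the log-RR scale:

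- SE = √(0.95/(1280 × 0.05) + 0.965/(1280 × 0.035)) = 0.1907
- Power = Φ((0.1398 + 0.3567)/0.1907 - 1.96) = Φ(0.643) = 74.0%

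A linearised ratio gives 73.6%, the ratio-scale score test 74.6% and simulation 74.5%. On the ratio scale, 80% power needs 1,465 to 1,498 per group, depending on the method.

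**3. The stated rule under no effect.** SE = √(2(1 - p)/(1280p)); power = Φ(0.1398/SE - 1.96).

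| Rate in both groups | SE | Power |
|---|---|---|
| 5% | 0.1723 | Φ(-1.149) = 12.5% |
| 3.5% | 0.2076 | Φ(-1.287) = 9.9% |

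At 5%, the other methods give 12.5% (linearised), 12.7% (ratio score), 12.9% (simulation) and 13.8% (risk difference). With rates near 5%, the observed RR must be at most about exp(0.1398 - 1.96 × 0.1723) = 0.82 to pass.

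The sample size for 80% power with both groups at 5% is (1.96 + 0.8416)² × 2 × (0.95/0.05) / 0.1398², about 15,270 per group.

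**4. Clustering.** 2,560/14 is about 183 samples per unit. The documents give no intraclass correlation for Aim 1B, so the Aim 1A values are assumed here, with the unit as cluster.

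| ICC | Design effect | Effective n per group | Power, 5% in both | Power, 3.5% vs 5% |
|---|---|---|---|---|
| 0.001 | 1 + 182 × 0.001 = 1.182 | 1,083 | 11% | 67% |
| 0.01 | 1 + 182 × 0.01 = 2.82 | 454 | 7% | 34% |

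**5. Would the count do better?** The documents give no mean or spread for CFU, so the coefficient of variation (CV) is an assumption. With independent samples and a true ratio of 1, the SE of the log ratio of means is CV × √(2/1280) = 0.0395 × CV.

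| CV | Power at margin 1.15 |
|---|---|
| 1.0 | 94% |
| 1.5 | 65% |
| 2 | 42% |
| 3 | 22% |

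Power reaches 80% only if the CV is at most 0.1398/(2.8016 × 0.0395), about 1.26. It equals that of the cut-off at CV = √(0.95/0.05), about 4.4.

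**The case against.** The 80% is openly conditional: section 6.2 says that the rates come from pilot data and that the power holds under those assumptions. The stated sample size can be reproduced, so a reader who infers an arithmetic error goes too far. That stands. It does not help the case of no effect, for which no power is given, nor the mismatch between a sample size that fits a risk difference and a decision rule on the relative risk.

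CFU > 30 is also a dichotomy of the measure named in the hypothesis, and section 2 speaks of contamination without naming the count. So the endpoint does not contradict the hypothesis. The documents do not explain the cut-off of 30, but nothing in them shows it to be wrong.

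A reader might go further and infer that the count should be primary, because it is already collected and would settle the question. The documents do not support this. Frequency of heavy contamination and average load are different questions, and a ratio of means can be driven by a few extreme plates. Without the CFU spread, the gain in power could be large or nil.

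A reader might also infer that the trial is bound to fail. That is too strong as well: 12.5% applies at a true RR of exactly 1, and at the pilot-based rates the figure is about 74% before clustering. Finally, nothing in the plan treats failed non-inferiority as harm; it is silent on the interpretation.

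**Conclusion.** The point holds as a fault in the stated power. The 80% in section 6.2 does not apply under the trial's own hypothesis. With 1,280 independent samples per group and the RR < 1.15 rule, power is about 12.5% if both groups are at 5% and about 10% if both are at 3.5%. At the planned 3.5% against 5% it is about 74%. If the Aim 1A intraclass correlations carry over, clustering reduces these to between 11% and 7% (5% in both groups) and between 67% and 34% (3.5% against 5%).

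The independent-sample figures rest only on rates, margin and numbers in the documents. The clustering figures rest on a borrowed intraclass correlation and should be read as a range. The case for a different primary endpoint is not established.

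**What to change.** In section 6.2, Aim 1B:

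- Restate the power for CFU > 30 under the relative-risk confidence-interval rule, both at the pilot-based rates (about 74%) and at equal rates (about 12.5% at 5%, about 10% at 3.5%).
- Show the effect of clustering, with the assumed intraclass correlation stated.
- Name the method and scale behind 1,280, so that sample size and decision rule agree.

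In section 6.1, state that an upper limit at or above 1.15 on CFU > 30 is inconclusive and is not by itself evidence of more contamination.

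These are changes of wording and calculation only, with no new samples or plates. The cost is a less favourable stated power.

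As an option, the sponsor could examine the CFU distribution in the pilot before deciding whether the already planned ratio of means (margin 1.15) should become primary. It reaches 80% power under no effect only with a CV of about 1.26 or less, and beats the cut-off only below about 4.4, in both cases before clustering. That change would cost more than wording: a new power calculation, a rule for very high plates, and acceptance that the primary question becomes one of average load.
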